Non-Interventional Study (NIS) Protocol

Document Number:	c41847952-01	
BI Study Number:	1199-0526	
BI Investigational Product(s):	Nintedanib	
Title:	Assessment of the Dose Reduction and Discontinuation associated with Anti-Fibrotic Medications in Patients with Idiopathic Pulmonary Fibrosis	
Brief lay title:	Dose Reduction and Discontinuation with Anti-Fibrotic Medications	
Protocol version identifier:	1.0	
Date of last version of protocol:	Not applicable	
PASS:	Pending	
EU PAS register number:	Pending	
Active substance:	NA NA	
Medicinal product:	Nintedanib (Ofev) and Pirfenidone (Esbriet)	
Product reference:	NA NA	
Procedure number:	Not applicable	
Marketing authorisation holder(s):	NA NA	
Joint PASS:	Not applicable	
Research question and objectives:	Primary aim - To assess average daily dose, and dose reduction/interruption patterns in nintedanib and pirfenidone initiators separately at 6- and 12- months post-initiation.	
	2. Secondary aim - To assess drug discontinuation patterns in nintedanib and pirfenidone initiators separately at 6- and 12-months post-initiation.	

NIS Protocol Page 2 of 36

Study number: 1199-0526 Document number: c41847952-01

Proprietary confidential information © 2023 Boehringer Ingelheim International GmbH or one or more of its affiliated companies

Country(-ies) of study:	United States		
Authors:			
Marketing authorisation holder(s):	Not applicable		
Date:	24 MAR 2023		
	Page 1 of 36		
Proprietary confidential information			

© 2023 Boehringer Ingelheim Group of companies. All rights reserved.

This document may not - in full or in part - be passed on, reproduced, published or otherwise used without prior written permission

NIS Protocol Page 3 of 36

Study number: 1199-0526 Document number: c41847952-01

Proprietary confidential information © 2023 Boehringer Ingelheim International GmbH or one or more of its affiliated companies

2. LIST OF ABBREVIATIONS

ADR Adverse Drug Reaction

AE Adverse Event

AESI Adverse Event of Special interest

CA Competent Authority
CCDS Company Core Data Sheet

CI Confidence Interval
CML Local Clinical Monitor
CRA Clinical Research Associate

CRF Case Report Form

CTCAE Common Terminology Criteria for Adverse Events

CTP Clinical Trial Protocol

eCRF Electronic Case Report Form

ENCePP European Network of Centres for Pharmacoepidemiology and

Pharmacovigilance

FDA Food and Drug Administration

GCP Good Clinical Practice

GEP Good Epidemiological Practice

GPP Good Pharmacoepidemiology Practice GVP Good Pharmacovigilance Practices

IB Investigator's Brochure

IEC Independent Ethics Committee
IRB Institutional Review Board
MAH Marketing Authorization Holder

MedDRA Medical Dictionary for Regulatory Activities

NIS Non-Interventional Study

PASS Post-Authorization Safety Study

SAE Serious Adverse Event USD United States Dollar

NIS Protocol
Page 6 of 36
Study number: 1199-0526
Document number: c41847952-01

Proprietary confidential information © 2023 Boehringer Ingelheim International GmbH or one or more of its affiliated companies

4. ABSTRACT

Name of company	:		
Boehringer Ingelheim			
Name of finished medicinal product: Nintedanib (Ofev) and Pirfenidone (Esbriet)			
Name of active ingredient: Nintedanib (Ofev) and Pirfenidone (Esbriet)			
Protocol date:	Study number:	Version/Revision:	Version/Revision date:
24 MAR 2023	1199-0526		
Title of study:	Assessment of the Dose Reduction/Interruption and Discontinuation with Nintedanib and Pirfenidone Initiators in Patients with Idiopathic Pulmonary Fibrosis		
Rationale and background:	Antifibrotics have demonstrated an ability to slow IPF progression, if taken according to the recommended dosing and taken continuously, in both clinical trials and real-world evidence. Previous real-world studies have compared persistence/discontinuation patterns for nintedanib and pirfenidone and found similar persistence patterns for both drugs. However, these studies have failed to consider the differential dosing regimens between these two drugs and corresponding incidence of dose reduction/interruption. This study will assess both dose reduction/interruption and discontinuation patterns for nintedanib and pirfenidone among patients with IPF.		
Research question and objectives:	 Primary aim - To assess average daily dose, and corresponding dose reduction/interruption patterns in nintedanib and pirfenidone initiators separately at 6- and 12-months post-initiation. Secondary aim - To assess drug discontinuation patterns in nintedanib and pirfenidone initiators separately at 6- and 12-months post-initiation. 		
Study design:	This is a non-interventional, retrospective cohort study with existing data.		

NIS Protocol Page 8 of 36

Name of company	: :		
Boehringer Ingelheim			
Name of finished medicinal product: Nintedanib (Ofev) and Pirfenidone (Esbriet)			
Name of active ing Nintedanib (Ofev) a Pirfenidone (Esbrie	and		
Protocol date: 24 MAR 2023	Study number: 1199-0526	Version/Revision:	Version/Revision date:
Population:	The study sample will consist of patients with IPF who initiated either nintedanib or pirfenidone between October 2014 to September 2021. The study will use data from the Optum Research Database (ORD), a claims database containing approximately 14 million commercial enrollees and 4 million Medicare-advantage enrollees		
Variables:	The main outcome of our study will be incidence of dose reduction/interruption, calculated separately for nintedanib and pirfenidone. For each patient, average daily dose will be calculated in pre-specified time-periods (for example – the first 6 months, the first 12 months, and the average daily dose calculated separately in each month since drug initiation). Incidence of dose reduction/interruption will be defined as average daily dose not following the prescribing information.		
	As a secondary outcome, we will also assess drug discontinuation during first 6 and 12 months separately for pirfenidone and nintedanib and will be defined as a gap of at least 60 days in filling of prescription (a gap of 60 days after the prescription date + days of supply for the current prescription).		
Data sources:	We will use administrative health insurance claims data from the Optum Research Database (ORD) for the period of October 1, 2013 through end of data availability (currently September 30, 2022). This database was chosen as it includes claims of Medicare Advantage and commercially enrolled beneficiaries.		
Study size:	As this is a descriptive study, no formal calculation of sample size was performed. In a preliminary feasibility analysis using Optum data to examine sample size, we have found that 1,979 patients newly		

NIS Protocol Page 9 of 36

Name of company:			
Boehringer Ingelheim			
Name of finished medicinal product: Nintedanib (Ofev) and Pirfenidone (Esbriet)			
Name of active ing Nintedanib (Ofev) : Pirfenidone (Esbrie	and		
Protocol date:	Study number:	Version/Revision:	Version/Revision date:
24 MAR 2023	1199-0526		
	initiated pirfenidone, and 2,559 patients who initiated nintedanib between 10/2014 to 12/2020. As such, this study is expected to have a sufficient sample.		
Data analysis:	Average daily dose during first 6 months and 12 months after drug initiation will be reported as means with standard deviations (SD), and median with interquartile range. Six months and 12-months daily dose categories will be presented as frequencies with percentages. Incidence of dose reduction/interruption will be reported by month of occurrence (using month 2 and onwards) and reported as frequencies with percentages. Drug discontinuation will be reported as frequencies with percentages, and time to drug discontinuation will be reported in months (mean (SD)). As this is a descriptive study, there will be no multivariable adjustment and/or direct comparison of outcomes between the pirfenidone and nintedanib cohort.		
Milestones:	The analytic database is expected to be constructed by April 20, 2023, and data analyses are expected to be completed by May 15, 2023. A draft report of the findings from this study is expected to be available for review by June 15, 2023 and completed by August 30, 2023.		

NIS Protocol Page 10 of 36

Study number: 1199-0526 Document number: c41847952-01

Proprietary confidential information © 2023 Boehringer Ingelheim International GmbH or one or more of its affiliated companies

5. AMENDMENTS AND UPDATES

None.

NIS Protocol Page 11 of 36

Study number: 1199-0526 Document number: c41847952-01

Proprietary confidential information © 2023 Boehringer Ingelheim International GmbH or one or more of its affiliated companies

6. MILESTONES

Milestone	Planned Date
First draft of summary	09/26/2022
AET summary review	10/17/2022
NPCC summary review	12/02/2022
Study protocol first draft	01/31/2023
NIS disclosure review	02/28/2023
Analytical database creation	04/20/2023
Descriptive results	05/15/2023
Final report first draft	06/15/2023

NIS Protocol Page 12 of 36

Study number: 1199-0526 Document number: c41847952-01

Proprietary confidential information © 2023 Boehringer Ingelheim International GmbH or one or more of its affiliated companies

7. RATIONALE AND BACKGROUND

Idiopathic pulmonary fibrosis (IPF) is a life-threatening rare disease characterized by decline in lung function due to progression of fibrosis in the interstitium of the lung [1]. In patients with IPF, a decline in forced vital capacity (FVC) is an important indicator of mortality [6]. The median survival of non-treated IPF patients is approximately 3 years from diagnosis [2].

[figure not shown]
Before anti-fibrotic medications became available in the US, IPF treatment mainly consisted of therapeutics that were found not to be of benefit (or even harmful), and a mainstay of care focused on symptom relief and included palliative care [3]. In October 2014, two anti-fibrotic medications, nintedanib and pirfenidone, were approved by the U.S. Food and Drug Administration (FDA) for the treatment of IPF [4, 5], which transformed the treatment of this disease. Both medications were found to reduce the rate of decline in FVC compared to placebo in phase III clinical trials [7, 8].

From the perspective of treatment, the approvals of antifibrotics for IPF were significant breakthroughs. Antifibrotics have demonstrated an ability to slow IPF progression, if taken according to the recommended dosing in the prescriber information and taken continuously, in both clinical trials [7, 8] and real-world evidence [9]. Previous real-world studies have compared persistence/ discontinuation patterns for pirfenidone and nintedanib and found similar persistence patterns for both drugs [10, 11]. However, these studies have failed to consider the differential dosing regimens between these two drugs and corresponding incidence of dose reduction and/or temporary dose interruption. Hence, this study will assess both dose reduction and/or temporary dose interruption and discontinuation patterns for pirfenidone and nintedanib among patients with IPF.

In this study, we will investigate the incidence of dose reduction/interruption beyond the label recommendations (defined as a dose not following the prescriber information (PI), which corresponds to a daily dose of 2165 mg (90% of full dose, which is 2403 mg) for pirfenidone [12, 13] or less than a daily dose of 200 mg for nintedanib (66.67% of full dose, which is 300 mg) [14]) from 10/01/2014 to 09/30/2022 using real-world data. The definition of incidence of dose reduction, which is differential for nintedanib and pirfenidone is because of –

- 1) In the US, the prescriber information (PI) and/or label for pirfenidone does not indicate any particular dose reduction recommended as per Food & Drug Administration (FDA). For nintedanib, reducing dose from 150 mg to 100 mg BID is part of the PI.
- 2) The post-hoc analysis of clinical trials showed similar slope of FVC decline for patients who reduced the dose to 100 mg BID for nintedanib, but for pirfenidone, the slope of FVC decline was steeper for patients who reduced the dose, potentially indicating that reduced dose might lead to lower benefit on FVC decline (see figures below) [12, 15]

Proprietary confidential information © 2023 Boehringer Ingelheim International GmbH or one or more of its affiliated companies

The current study may be able to demonstrate to decision makers the differential complexities in dosing regimen for pirfenidone vs. nintedanib and may reveal that IPF patients may not be receiving the full benefit of pirfenidone due to possible sub-optimal dosing, even when the patient has not discontinued the drug.

NIS Protocol Page 14 of 36

Study number: 1199-0526 Document number: c41847952-01

Proprietary confidential information © 2023 Boehringer Ingelheim International GmbH or one or more of its affiliated companies

8. RESEARCH QUESTION AND OBJECTIVES

The overarching aim of our study is to assess the incidence of dose reduction and discontinuations separately for pirfenidone and nintedanib. Specific objectives are:

Primary aim - To assess average daily dose, and corresponding dose reduction/interruption patterns in pirfenidone initiators and nintedanib initiators separately at 6- and 12- months post-initiation.

Secondary aim - To assess drug discontinuation patterns in pirfenidone initiators and nintedanib initiators separately at 6- and 12-months post-initiation.

001-MCS-90-118_RD-23 (1.0) / Saved on: 25 Nov 2019

NIS Protocol Page 15 of 36

Study number: 1199-0526 Document number: c41847952-01

Proprietary confidential information © 2023 Boehringer Ingelheim International GmbH or one or more of its affiliated companies

9. RESEARCH METHODS

9.1 STUDY DESIGN

This study will be a retrospective cohort, descriptive study of patients with idiopathic pulmonary fibrosis (IPF). Patients with IPF who initiated either pirfenidone or nintedanib between October 2014 to September 2021 will be identified. The study will use data from the Optum Research Database (ORD), a claims database containing approximately 14 million commercial enrollees and 4 million Medicare-advantage enrollees. The date of the first prescription of either pirfenidone or nintedanib will be assigned as index date. Two separate cohorts will be created - 1) pirfenidone initiators, and 2) nintedanib initiators, and all outcomes will be assessed in the 12 months post-index period. A 12-month time-period prior to the index date will be used as the baseline period for determining the characteristics of patients in both cohorts. To allow for a 12-months baseline and follow-up periods for all patients, the span of data will be from 10/01/2013 to 09/30/2022. (Figure 1)

[figure not shown]

Figure 1 Study Design Schematic

The main outcome of our study will be incidence of dose reduction/interruption, calculated separately for pirfenidone and nintedanib. For each patient, average daily dose will be calculated in pre-specified time-periods (for example – the first 6 months, the first 12 months, and the average daily dose calculated separately in each month since drug initiation) (more details in section 2.6). Incidence of dose reduction/interruption will be defined as average daily dose not following the prescribing information (PI). According to the PI, the daily dose of pirfenidone is 2403 mg [13], hence the study will consider average daily dose less than 2165 mg (90% of PI dose) as dose reduction for pirfenidone [12]. For nintedanib, the daily dose allowed under prescriber information is 200 mg [14], hence less than 200 mg will be considered a dose reduction for nintedanib patients. As a secondary outcome, we will also assess drug discontinuation during first 6 and 12 months separately for pirfenidone and nintedanib and will be defined as a gap of at least 60 days in filling of prescription (a gap of 60 days after the prescription date + days of supply for the current prescription). In a sensitivity analysis, we will explore 30- and 90- days gap as a definition for drug discontinuation. As this is a descriptive study, assessment of the dose reduction and discontinuation for both drugs will be considered separately, and only descriptively, without any direct comparison between the two cohorts.

NIS Protocol Page 16 of 36

Study number: 1199-0526 Document number: c41847952-01

Proprietary confidential information © 2023 Boehringer Ingelheim International GmbH or one or more of its affiliated companies

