9.3.2 Outcomes

9.3.2.1 Primary outcome

The main outcome measure of our study is the incidence of dose reduction/interruption, calculated separately for each drug. For calculating the primary outcome, we will first need to calculate the average daily dose of pirfenidone and nintedanib after drug initiation (post-index period). Specific details of calculations are —

Average daily dose

Average daily dose for each patient will be calculated by taking the average of total drug intake (tablet strength * number of doses) during the time between index date to the date of drug discontinuation

```
Average \ Daily \ Dose \\ = \frac{\sum_{0}^{n}(Tablet \ Strength*number \ of \ tablets \ in \ a \ Rx \ fill)}{Time \ of \ follow - up \{(Date \ of \ discontinuation) - Index \ Date\}} Where n = number of fills a patient has received for pirfenidone/nintedanib
```

- We will calculate average daily dose of pirfenidone and nintedanib separately for each month in post-index period (month 1 to 12) and will also calculate for cumulative periods of 6 months and 12 months. For all calculations, censoring events will be taken into account, with patient censored at the date of drug discontinuation, or end of 12 months.
- Six and twelve months average daily dose categories For the average daily dose calculations in cumulative periods, we will be dividing the patients in following 4 categories
 - 1) Dose strength less than 50%
 - 2) Dose strength between 51% to 66%
 - 3) Dose strength between 67% to 90%
 - 4) Dose strength above 90%

Incidence of Dose Reduction and/or temporary dose interruption

Once average daily dose is calculated for each month post-index (month 1 to 12), incidence of dose reduction/interruption will be calculated as presence of average daily dose $\leq 90\%$ dose strength (for pirfenidone) or $\leq 66.67\%$ dose strength (for nintedanib), as per the PI [12 – 14]. Patients will be required to have the dose reduction for at least for 60 days, to make sure that the dose reduction is not temporary.

In a sensitivity analysis, we will also evaluate temporary dose reductions, i.e., dose reduced to below the above defined dose strength only for 1 month.

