9.7.2 Post-hoc analysis

As this study is a descriptive analysis, no adjustments or direct comparison between pirfenidone and nintedanib cohort is proposed a-priori. If significant differences in the baseline characteristics between the pirfenidone and nintedanib cohorts are observed, we propose to conduct propensity score matching (PSM) to balance the baseline characteristics between the two cohort. Specifically, pirfenidone initiators will be matched to nintedanib initiators using the technique of nearest neighbor match on an estimated propensity score (caliper width of ±0.001 unit). The propensity score for this analysis will be obtained from a logistic regression model using pre-index measures to predict the probability of being in the pirfenidone initiator cohort. Pre-index measures which will be included are demographic (age, sex, census region, index year), clinical (CCI, pulmonary hypertension, COPD, asthma, GERD, HRCT scan, oxygen use, and ventilator use), and healthcare utilization measures (total pharmacy spend, total medical spend, number of pulmonology visits)

We will compare differences in baseline characteristics between the pirfenidone and nintedanib cohorts before and after propensity score matching. The success of the propensity score-matching to reduce confounding will be assessed by evaluating the standardized differences in the covariates between the study groups after matching. For each covariate, the standardized difference percent (di) will be calculated as: $di = 100 * (xi - xni) / \sqrt{(s2i + xni)}$

NIS Protocol Page 25 of 36

Study number: 1199-0526 Document number: c41847952-01

Proprietary confidential information © 2023 Boehringer Ingelheim International GmbH or one or more of its affiliated companies

s2ni}/2) where xi and xni are the sample means of the ith covariate in the pirfenidone and nintedanib cohorts, respectively, and s2i and s2ni are the corresponding sample variances. A standardized difference of <10% is considered an acceptable level of difference (or supports the assumption of balance) between the comparison groups.

We will reassess the primary and secondary outcomes in the matched cohorts (see Section 9.7.1 for more details)

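### The drug-specific dose-reduction cut-offs tolerate refill lateness unequally, and no common-cut-off version of the monthly 60-day outcome is planned

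*Combined protocol and SAP*

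**What the plan says.** Section 9.1 gives the pirfenidone reference dose ("According to the PI, the daily dose of pirfenidone is 2403 mg") and counts "average daily dose less than 2165 mg (90% of PI dose) as dose reduction for pirfenidone". For nintedanib it takes 200 mg as the daily dose the label allows, "hence less than 200 mg will be considered a dose reduction for nintedanib patients". Section 7 puts the nintedanib figure on a percentage scale: "daily dose of 200 mg for nintedanib (66.67% of full dose, which is 300 mg".

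The asymmetry is intended. Section 7 introduces its reasons with "The definition of incidence of dose reduction, which is differential for nintedanib and pirfenidone is because of" and names two: the nintedanib label includes a lower dose step while the pirfenidone label recommends no particular reduction, and post-hoc trial analyses showed different FVC slopes after reduction.

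Section 9.3.2.1 applies the cut-offs month by month and adds a duration rule: "Patients will be required to have the dose reduction for at least for 60 days". The only sensitivity analysis it names for dose reduction shortens the duration to one month and keeps the same cut-offs. The same section puts both drugs on a common percentage scale with breaks at 50, 66/67 and 90%, but only for the cumulative 6- and 12-month averages.

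Sections 9.1, 9.3.1 and 9.7.1 rule out direct comparison of the cohorts. Section 7 nevertheless says the study may be able to "demonstrate to decision makers the differential complexities in dosing regimen for pirfenidone vs. nintedanib". If baseline characteristics differ significantly, Section 9.7.2 proposes propensity matching and then: "We will reassess the primary and secondary outcomes in the matched cohorts". It sets no new cut-off.

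**The concern.** Dose is inferred from fills, and Section 9.9 concedes that fill-based dose may not be actual intake and that reduction cannot be told from interruption. A patient prescribed full dose throughout can therefore count as reduced merely by refilling late. Such a patient has about 10% slack on pirfenidone and 33% on nintedanib, so identical refill behaviour can yield different incidences.

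At stake is how the two headline incidences are read. They will appear in one report, possibly in matched cohorts, against a rationale that anticipates a pirfenidone versus nintedanib message. Matching balances patients; it cannot remove a difference that sits in the outcome definition. Without a common-scale version of the monthly outcome, a reader cannot tell how much of any contrast comes from the cut-offs.

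**Working it through.** **The plan's own figures.** 0.90 × 2403 = 2162.7 mg; the stated 2165 mg is 2165/2403 = 90.1%. 200/300 = 66.67%. Both reproduce, the first to within 0.1 percentage point.

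**Constant lateness, full dose, 30-day fills** (Section 9.3.2.2 calls 30 days typical). If every refill is *g* days late, the average over a fill cycle is 30/(30+*g*) of full dose.
- Pirfenidone: *g* = 3 gives 30/33 = 90.9%, not flagged; *g* = 4 gives 30/34 = 88.2%, flagged.
- Nintedanib: *g* = 14 gives 30/44 = 68.2%, not flagged; *g* = 15 gives 30/45 = 66.67%, flagged only if equality counts; *g* = 16 gives 30/46 = 65.2%, flagged.

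So 4 to 14 days late separates the drugs. In fixed 30-day months with supply spread day by day, a month holding one whole gap scores (30−*g*)/30. Pirfenidone is then flagged from *g* = 3 (27/30 = 90%, or 2162.7 mg). Nintedanib is flagged from *g* = 11 (19/30 = 63.3%), or from *g* = 10 if equality counts (20/30 = 66.67%). The band becomes 3 to 9 days. Months 2 and 3 each hold a whole gap in these cases, so a two-month rule is met.

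**The reverse asymmetry.** A nintedanib patient at exactly 200 mg/day who refills one day late averages 66.67% × 30/31 = 64.5% of full dose and falls below the cut-off. With perfect refills the same patient is not reduced under Section 9.1 (below 200 mg) but is reduced under Section 9.3.2.1 (at or below 66.67%).

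**Simulated incidence.** Event: two adjacent 30-day months, within months 2 to 12, below the cut-off; 30-day fills; full dose. Late-only runs use exponential delays, with censoring at a 60-day gap. The documents give no refill-delay data, so every delay below is an assumption. Each cell shows the pirfenidone cut-off, then the nintedanib cut-off.

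| Fill allocation and delay model | Mean 1 day | Mean 2 days | Mean 3 days |
|---|---|---|---|
| Day by day, whole-day delays, one mean for all | 5.6% / 0.0% | 50.6% / 0.0% | 79.8% / 0.4% |
| Day by day, continuous delays, one mean for all | about 2% / 0% | about 36% / 0.1% | about 67% / 0.5% |
| Day by day, mean delay varying between patients | 15.0% / 0.1% | 36.2% / 1.8% | 50.1% / 5.0% |
| Whole fill credited to dispensing month, mean delay varying between patients | 0.0% / 0.0% | 0.2% / 0.2% | 1.0% / 1.0% |

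In the last row the gap is nil because a full-dose month scores either zero or at least 100%, so both cut-offs flag the same months.

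If refills can be early (intervals normal around 30 days, SD 4, surplus carried forward), the pirfenidone cut-off flags about 18% when fills average on time, 7% at one day early and 2% at two days early.

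For nintedanib patients at exactly 200 mg/day, day-by-day allocation with late-only refills and one mean for all flags 95-100% at mean delays of 1 to 3 days, even under the strict below-200 rule.

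**The case against.** The strongest reply is that the outcome is departure from the label, not relative dose intensity. Applying 90% to nintedanib would flag a dose that Section 7 describes as part of the label, which answers a different question. That stands, and is why the primary definition should stay.

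Second, the plan already has a common scale at 6 and 12 months, the time points of the primary aim, and repeatedly disclaims comparison. This mitigates the problem but does not close it. A cumulative average is not the monthly 60-day incidence, the category edges leave 66.67% itself unassigned, and the disclaimer is not restated for outcomes in the matched cohorts.

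Third, the simulated gaps rest on invented delays and on an allocation rule the protocol does not state. This also stands: the range includes zero, and simulating only full-dose patients maximises the contrast.

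Fourth, a shared cut-off would still count late refills as reductions. True: it equalises tolerance and does not remove the misclassification.

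A reader might go further and infer that the cut-offs are an error, that most of any observed difference will be artefact favouring nintedanib, or that a comparison is planned outright. The documents do not support these readings. Reasons for the cut-offs are given, the dose mix and refill pattern are unknown, patients at 200 mg/day push the other way, and the matched analysis is conditional with no comparison proposed in advance.

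**Conclusion.** The point holds as a missing sensitivity analysis and an interpretation risk, not as a fault in the primary definition. What is firm is the arithmetic: at full dose with 30-day fills, consistent lateness of 4 to 14 days on the cycle average, or 3 to 9 days in fixed 30-day months, separates the drugs, while a patient at exactly 200 mg/day of nintedanib has almost no slack.

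What is not firm is the effect on reported incidence. With assumed mean delays of 1 to 3 days it runs from no gap to roughly 2-80% against 0-1%. The nintedanib figure reaches 5% if mean delay varies between patients, and the gap shrinks if refills are sometimes early. Net size and direction in the real cohorts cannot be derived from the documents. The change should be made because it is cheap and determines whether the two incidences can be read side by side.

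**What to change.** 1. Keep the drug-specific primary definition.
2. Pre-specify one sensitivity table that applies both existing cut-offs (90% and 66.67%) to both drugs for the monthly 60-day outcome, in the full cohorts and in any matched cohorts.
3. State one rule for allocating a fill's supply to months, including early refills and carried-over supply, and use it throughout.
4. Extend the no-comparison statement explicitly to the drug-specific incidences in the Section 9.7.2 re-analysis.
5. Reconcile Section 9.1 (below 200 mg) with Section 9.3.2.1 (at or below 66.67%), because they classify a patient at exactly 200 mg/day differently.

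Cost: one extra table from variables already derived, plus a few sentences. The table must be labelled as relative dose intensity rather than departure from the label, and the contrast between drugs may look smaller.

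### The pirfenidone cut-off leaves about 10% tolerance below its label dose and the nintedanib cut-off leaves none below the label-permitted 200 mg/day, so repeated small refill delays can create nintedanib events

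*Combined protocol and SAP*

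**What the plan says.** Section 9.1 defines the main outcome as an average daily dose that departs from the prescribing information (PI), then sets one cut-off per drug.

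- Pirfenidone: "According to the PI, the daily dose of pirfenidone is 2403 mg", and "hence the study will consider average daily dose less than 2165 mg (90% of PI dose) as dose reduction for pirfenidone".
- Nintedanib: "For nintedanib, the daily dose allowed under prescriber information is 200 mg", and "hence less than 200 mg will be considered a dose reduction for nintedanib patients".

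Section 7 confirms that the lower nintedanib dose is on label: "For nintedanib, reducing dose from 150 mg to 100 mg BID is part of the PI". It gives the same cut-off as a percentage: "less than a daily dose of 200 mg for nintedanib (66.67% of full dose, which is 300 mg").

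Section 9.3.2.1 computes average daily dose as dispensed strength times tablets, divided by elapsed time, for each of months 1 to 12 and cumulatively. There the nintedanib rule is at or below 66.67% of dose strength, not strictly below 200 mg. The reduction must last at least 60 days to count in the primary analysis; a one-month reduction goes to a sensitivity analysis. Section 9.3.2.2 gives the usual supply per fill as 30 days.

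**The concern.** The two cut-offs sit at different distances from the doses that the plan itself treats as on label. A patient on full-dose pirfenidone can lose about a tenth of the dispensed dose to refill timing before a month is flagged. A patient on 100 mg BID can lose nothing: without early refills the monthly average cannot exceed 200 mg, and any uncovered day takes it lower.

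For these patients the event partly measures refill punctuality rather than departure from the PI. That would misclassify on-label patients within the nintedanib cohort, whether or not the drugs are compared. It would also carry into the conditional matched-cohort analysis in Section 9.7.2, because matching on baseline characteristics does not remove a difference in how the outcome is defined.

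**Working it through.** **Inputs.** Pirfenidone PI dose 2403 mg and cut-off 2165 mg (Section 9.1); nintedanib full dose 300 mg (Section 7) and cut-off 200 mg (Sections 7 and 9.1); 30-day fills (Section 9.3.2.2); 60-day rule (Section 9.3.2.1). Late-refill rates are not in the documents and are assumed below.

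**Step 1: the plan's own figures.** 0.90 × 2403 = 2162.7 mg. The stated 2165 mg is 2165/2403 = 90.1%, so it is reproduced apart from rounding. 200/300 = 66.67%, also reproduced.

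**Step 2: margin below the on-label dose.**

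- Pirfenidone: 2403 − 2165 = 238 mg, or 238/2403 = 9.9%.
- Nintedanib 100 mg BID: 200 − 200 = 0 mg.
- Nintedanib 150 mg BID: (300 − 200)/300 = 33.3%.

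**Step 3: one refill interval.** Average = daily dose × 30 / interval in days.

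| Interval (days) | Pirfenidone, full dose (mg) | Below 2165? | Nintedanib 100 mg BID (mg) | Below 200? | Below 180? |
|---|---|---|---|---|---|
| 30 | 2403.0 | no | 200.0 | no | no |
| 31 | 2325.5 | no | 193.5 | yes | no |
| 33 | 2184.5 | no | 181.8 | yes | no |
| 34 | 2120.3 | yes | 176.5 | yes | yes |

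Here 180 mg is 0.90 × 200, the same 10% allowance (180/300 = 60% of full dose). With it the two drugs change status at the same interval. Nintedanib 150 mg BID reaches 200 mg at 45 days (300 × 30/45) and falls below it only after that.

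**Step 4: apply the 60-day rule.** Take 30-day months, count supply by day, and require two consecutive months below the cut-off.

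- One refill one day late on 100 mg BID: one month at 200 × 29/30 = 193.3 mg, the rest at 200 mg. This is not a primary event, but it is an event in the one-month sensitivity analysis.
- Two consecutive refills each one day late: two months at 193.3 mg, a primary event.
- Pirfenidone with the same delays: 2403 × 29/30 = 2322.9 mg, never flagged.

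**Step 5: illustrative frequency.** Let each refill be late independently with probability p, by 1-3 days with equal chance, and count months 2 to 12. On 100 mg BID any late day flags the month, so the monthly flag probability is f = p. On pirfenidone only three uncovered days do so, because 2403 × 27/30 = 2162.7 is just under 2165; hence f = p/3. The chance of no two consecutive flagged months follows a(n) = (1−f)·a(n−1) + f(1−f)·a(n−2), with a(0) = a(1) = 1, and the event probability is 1 − a(11). Simulation of 20,000 patients per setting agrees.

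| p | 100 mg BID, below 200 mg | Pirfenidone, below 2165 mg | 100 mg BID, below 180 mg |
|---|---|---|---|
| 10% | 9% | 1% | 0% |
| 20% | 30% | 4% | 0% |
| 30% | 54% | 9% | 0% |

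For at least one flagged month (the one-month sensitivity analysis), 1 − (1−f)^11 gives 69%, 91% and 98% on 100 mg BID, and 31%, 53% and 69% on pirfenidone.

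**Step 6: vary the assumptions.**

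- Delays of exactly one day: 9%, 30% and 53% on 100 mg BID; 0% on pirfenidone.
- Delays of 1-7 days at p = 20%: about 30% (100 mg BID, below 200 mg), 17% (pirfenidone) and 11-12% (100 mg BID, below 180 mg).
- 40% of refills 1-3 days early with supply carried forward: about 4%, 13% and 27% on 100 mg BID.
- Each fill credited wholly to the month of its fill date: 0% at all three rates.

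**Step 7: the competing wording.** Under Section 9.3.2.1, 200/300 = 66.667% satisfies a rule of at or below 66.67%. A patient on 100 mg BID for 60 days is then an event with every refill on time.

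**The case against.** The strongest reply is that the definitions differ on purpose. Section 7 says so and gives two reasons: the nintedanib label includes a reduced dose, and trial post-hoc analyses showed different FVC slopes after dose reduction. The 90% is attributed to a pooled pirfenidone dose-intensity analysis, and the plan nowhere describes it as an allowance for refill timing. This stands as an account of why 200 mg is the nintedanib anchor. It does not explain why there is no tolerance below that anchor, and whatever its origin the 90% acts as a tolerance.

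A reader might infer that one refill a day late puts a patient on 100 mg BID among the primary events. The documents do not support that: the 60-day rule in Section 9.3.2.1 sends an isolated low month to the sensitivity analysis only.

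The size is also open to challenge, and most of that challenge stands. Late-refill rates are assumed, early refills shrink the effect, and crediting fills to their fill month removes it. The 0% at 180 mg arises because delays are capped at three days and 27/30 is exactly 90%. The pirfenidone figures under 1-3 day delays arise because 2165 mg is 90.1%; at exactly 90% they would be 0%.

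Finally, Section 9.9 concedes that fill-based dose may differ from intake, cumulative dose is also summarised, and the main analysis makes no direct comparison. The concession does not remove misclassification inside the nintedanib cohort, and Section 9.7.2 leaves matched cohorts open.

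**Conclusion.** The asymmetry is in the text and holds: 9.9% below the label dose for pirfenidone, 0% below the label-permitted 200 mg/day for nintedanib. Patients dispensed 100 mg BID throughout can become primary events when small refill delays leave uncovered days in two consecutive months. Pirfenidone patients with the same one-day delays cannot.

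The illustrative 9%, 30% and 54% apply only to patients always on 100 mg BID. They rest on 30-day fills, day-by-day counting within months, independent delays and no early refills. It would be tempting to conclude that nintedanib incidence as a whole is inflated by a known amount. The documents do not support that, because they give neither the 100 mg BID share nor a late-refill rate, and patients on 300 mg/day have a wider margin than pirfenidone patients. For scale only: if 10-40% were on 100 mg BID throughout and 20% of refills were late, the excess would be 0.10 × 30% = 3 to 0.40 × 30% = 12 percentage points.

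Nor do the documents show that 180 mg must replace 200 mg as the primary cut-off. The 200 mg rule follows directly from the plan's definition of the event. What is needed is a consistent rule, a stated allocation, and a row showing how much of the nintedanib result depends on refill timing.

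**What to change.** 1. Reconcile Section 9.3.2.1 (at or below 66.67%) with Sections 7 and 9.1 (below 200 mg), so that the status of exactly 200 mg/day is unambiguous. This comes first, but settling on strictly below 200 mg would still leave zero margin for refill timing.
2. Pre-specify nintedanib incidence with the same 90% tolerance on dispensed dose (average below 180 mg/day, 60% of full dose), at least as a sensitivity row beside below 200 mg. Use the equal-tolerance version in any matched-cohort analysis under Section 9.7.2.
3. State in Section 9.3.2.1 how fills, carried-over supply and uncovered days are allocated to months.

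These are analysis thresholds on dispensed drug, not dosing rules. The cost is some protocol wording and one extra table row. The downside is that averages from 180 mg/day up to just under 200 mg/day are not events in that row; the 200 mg row beside it still shows them. The added row also does not absorb longer delays.
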